3.3. Exclusion Criteria

1. Patients with untreated or uncontrolled infections
2. Patients with untreated or uncontrolled grade 3 or 4 GVHD
3. Pregnancy and lactation
4. Concurrent use of any other investigational agents.
5. Known HIV-positive patients.
6. Known hypersensitivity to 5AC or GM-CSF

3.4. Inclusion of Women and Minorities

The proposed study is open to both men and women and to all racial/ethnic subgroups. There is no explicit mention of different treatment effects in male and female patients or in different racial/ethnic subgroups in the literature. Therefore, this study will not have separate accrual targets for these groups.

3.5. Off-study Criteria

Patients may be removed from the study for any of the following:

1. Death
2. Completion of follow-up as per section 5.4
3. Elective withdrawal of consent by patient

3.6. Informed Consent

All patients eligible for the study must be evaluated by one of the study investigators. Informed consent must be obtained and the consent form signed. A Johns Hopkins On-Study Form will be completed following fulfillment of the on-study requirements for laboratory work and eligibility criteria. For enrollment of non-English-speaking candidates, the policies and procedures mandated by the JH IRB will be followed as listed at the following website: <https://irb.jhmi.edu/Guidelines/nonenglishconsent.html>

4. Pretreatment Plan

A complete history and physical examination and list of medications will be documented for each patient within two weeks of enrollment. A bone marrow aspirate or biopsy confirming the suspected diagnosis will be documented in the electronic medical records. Bone marrow aspirate / biopsy documenting no evidence of leukemia will be performed after completion of therapy. Evaluations within 14 days of beginning therapy will include:

1. A history and physical exam, including a list of active medications
2. Hematologic studies: complete blood count with platelet and differential cell counts.
3. Chemistry panel (including electrolytes, creatinine, uric acid, albumin, total protein, calcium and phosphate)
4. Hepatic panel: serum SGOT, SGPT, alkaline phosphatase, total bilirubin, PT/PTT.
5. Reticulocyte count
6. An EKG

5. Treatment Plan

5.1. Treatment Schedule

The planned initial dose of 5AC is $37.5\text{mg}/\text{m}^2$ (Level 0) and this will be administered subcutaneously or intravenously for days 1 through 5 of a 28 day cycle. Patients who tolerate the combination with no SAEs during two consecutive cycles will be eligible for a dose escalation to $50\text{mg}/\text{m}^2/\text{day}$ for 5 days of every 28 day cycle (Level +1). Patients who tolerate Dose Level +1 with no SAEs during two consecutive cycles will be eligible for a dose escalation to $75\text{mg}/\text{m}^2/\text{day}$ for 5 days of every 28 day cycle (Level +2). Patients will

continue at Dose Level +2 for the study’s duration provided there are no toxicities requiring dosing delays or dose reduction.

Dose reductions are permitted as per the standard treatment approach with 5AC and are listed below in Table 2. Patients who experience toxicity or dosing delays, but return to pre-therapy baseline within 56 days of the first day of their most recent cycle, will be eligible to continue at the next lower Dose Level (Table 2). Patients unable to tolerate the lowest dose of 12.5mg/m² /day for 5 days (Dose Level -2) due to toxicities or cytopenias, will be removed from the study. Patients requiring a dose reduction are not eligible for re-escalation. Azacitidine dosing is the same regardless of subject age.

Table 2

Dose Level	5AC
-2	12.5mg/m ²
-1	25mg/m ²
0	37.5mg/m² (starting dose level)
+1	50mg/m ²
+2	75mg/ m ²

GM-CSF will be self-administered subcutaneously for days 1-10 of each 28 day cycle. For subjects unable to self-administer, GM-CSF may be administered by a caregiver or on site at Johns Hopkins or a local provider’s office. Dosing will be based on weight and rounded to a standard dosing size: patients who weigh less than or equal to 70kg will receive 125 micrograms/day and those who weigh over 70kg will receive 250 micrograms/day. Pediatric subjects will receive 125 micrograms/day regardless of weight. Subjects will be given prescriptions for pre-dosed syringes of GM-CSF. If the starting dose is not tolerated due to traditional side effects of GM-CSF, such as muscle aches and pains, bone or joint discomfort, or elevated WBC > 25,000, the drug will be held through resolution of these side effects. Patients who return to their pre-dosing baseline will re-start the GM-CSF at the next cycle start date at the next lower Dose Level (Table 3). Patients unable to tolerate the minimum dose (Dose Level -3) for 7 days due to either persistently elevated WBC or other side effects will be removed from the study.

Table 3

Dose Level	GM-CSF patients >18 years	Patients ≤ 18 years
-3	50micrograms x 7 D	50micrograms/ m ² x 7D
-2	50 micrograms x10 D	50micrograms/ m ² x 10D
-1	62.5 micrograms x 10D	62.5micrograms/ m ² x10D
0	125 micrograms (starting dose weight <70 kg) x 10D	125micrograms/ m² x10D¹
+1	250 micrograms (starting dose weight >70 kg) x 10D	

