5.2. Dosing Delays and Modifications for Toxicity

5.2.1. Dosing Delays for Hematologic Toxicity

If a patient develops critical drug induced neutropenia or thrombocytopenia (as defined in sections 5.22), 5AC and GM-CSF will be held. If neutrophil count rises to $100-500/\text{mm}^3$, or platelet count rises to $10,000-50,000/\text{mm}^3$, the patient may resume the next cycle at the next lower dose level. If the neutrophil count is greater than $500/\text{mm}^3$ or the platelet count greater than $50,000/\text{mm}^3$, the patient may resume the next cycle at the same dose level. If there is inadequate peripheral count recovery within 56 days from the first day of the most recent cycle the patient will be removed from the study and a bone marrow biopsy and aspirate will be performed.

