5.2.2. Definitions of Hematologic Toxicity

Critical neutropenia or thrombocytopenia is defined by a neutrophil count $<100/\text{mm}^3$ or a platelet count $<10,000/\text{mm}^3$. Persistent critical cytopenias are those that last for greater than 3 weeks.

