5.2.4. Non-hematologic Adverse Events

Patients with grade 3 or 4 non-hematological adverse event, deemed by the investigator to be possibly, probably or definitely related to the study drugs, will hold both 5AC and GM-CSF through the start of the next planned cycle. If the adverse events resolve to pre-treatment baseline, the study drugs will be resumed starting with the following scheduled cycle at the next lowest Dose Level. To allow for resolution of adverse events, patients may have study drugs held for up to 58 days from the start of the most recent cycle prior to being removed from the study.

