5.3. Duration of Therapy

Treatment is planned for a total of 12 cycles of therapy and will continue until one of the following occurs:

1. Disease relapse
2. Serious illness that prevents further administration of treatment (i.e., progressive infection not responding to appropriate antibacterial and/or anti-fungal therapies)
3. Unacceptable adverse event(s)

4. Elective withdrawal of consent by the patient
5. Determination by the physician that it is no longer in the patient's best interest to continue on trial
6. Delay of the study drug dose for more than 56 days from the first day of the most recent cycle due to unresolved toxicities
7. Inability to tolerate either study drug at the lowest allowable dose levels
8. Initiation of breast feeding by the patient.
9. Patient pregnancy

All subsequent cycles may be initiated no sooner than 28 days and no later than 56 days from Day 1 of the previous cycle.

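### Maximum hold after toxicity is 58 days in section 5.2.4 but 56 in 5.3, and sections 5.1 and 5.2.1 disagree on recovery and restart level after critical cytopenia

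*Combined protocol and SAP*

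**What the plan says.** All references are to the combined protocol and SAP.

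- **Section 5.1** covers toxicity and dosing delays in general. The patients who may go on are described as "Patients who experience toxicity or dosing delays, but return to pre-therapy baseline within 56 days of the first day of their most recent cycle"; they "will be eligible to continue at the next lower Dose Level". The section also bars re-escalation once a dose reduction has been needed.
- **Section 5.2.2** sets the trigger for a hematologic hold: "Critical neutropenia or thrombocytopenia is defined by a neutrophil count" below 100/mm³ or a platelet count below 10,000/mm³.
- **Section 5.2.1** says what follows. With neutrophils of 100-500/mm³ or platelets of 10,000-50,000/mm³, "the patient may resume the next cycle at the next lower dose level". With neutrophils above 500/mm³ or platelets above 50,000/mm³, "the patient may resume the next cycle at the same dose level". Removal follows "inadequate peripheral count recovery within 56 days from the first day of the most recent cycle".
- **Section 5.2.4** covers drug-related grade 3 or 4 non-hematologic events. The event must resolve to the pre-treatment baseline and the restart is at a lower level. Before removal, "patients may have study drugs held for up to 58 days from the start of the most recent cycle".
- **Section 5.3** lists, as a reason to end treatment, a delay of more than 56 days from the first day of the latest cycle because of unresolved toxicity. It adds: "All subsequent cycles may be initiated no sooner than 28 days and no later than 56 days from Day 1 of the previous cycle".

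No section says which of these takes precedence.

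**The concern.** These rules decide whether a patient stays on treatment after toxicity, and at what dose. On two matters a clinician who follows one section faithfully will break another.

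The first is the length of the hold for a non-hematologic event, where 5.2.4 uses 58 days and 5.3 and 5.1 use 56, all counted from the start of the latest cycle. The second is the recovery needed after critical cytopenia and the level at which treatment restarts, where 5.1 and 5.2.1 differ.

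At stake is consistency of dosing and discontinuation between patients. Describing the toxicity of the combination is the first secondary objective (section 1.2). Summaries of dose level reached, reductions and discontinuations for toxicity would partly reflect which section was applied.

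**Working it through.** There is no sample size, power or event count to reproduce. The check sets the rules side by side and applies them to example patients.

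**1. Maximum hold, non-hematologic event**

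Inputs: 58 days (5.2.4); 56 days (5.3, both the stopping reason and the cycle window); 56 days (5.1). All run from day 1 of the latest cycle.

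Gap: 58 − 56 = 2 days.

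| Event resolves | 5.2.4 | 5.3 | 5.1 |
|---|---|---|---|
| by day 56 | within hold | within limit | within limit |
| day 57 or 58 | within hold | treatment ends; next cycle too late | limit missed |
| after day 58 | removed | treatment ends | limit missed |

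Only the middle row conflicts. There is little slack below it. Section 5.2.4 holds both drugs through the next planned cycle start and resumes at the one after. With 28-day cycles that restart falls 2 × 28 = 56 days after day 1, exactly on the 5.3 limit.

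**2. Recovery needed after critical cytopenia**

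Inputs: trigger of neutrophils below 100/mm³ (5.2.2); restart permitted from 100/mm³ (5.2.1); return to pre-therapy baseline (5.1); entry neutrophils of at least 1000/µL (section 3.1).

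Patient A falls below 100/mm³ and recovers to 400/mm³ by day 56, with platelets no longer critical.

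- 5.2.1: 400 lies in the 100-500 band, so the patient may resume, at the next lower level on the neutrophil criterion.
- 5.1: if the pre-therapy count was at the entry level of 1000 or more, 400 is not baseline and the condition for continuing is not met.

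The result is continue under one section and not under the other.

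**3. Restart level after full recovery**

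Patient B has critical neutropenia and both counts return fully to baseline by day 56.

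- 5.2.1: neutrophils exceed 500/mm³, so the same level is allowed.
- 5.1: the baseline condition is met, and the only level offered is the next lower one.

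Size of one 5AC step, from Table 2:

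| Level before hold | Same level (mg/m²) | Next lower (mg/m²) | Reduction |
|---|---|---|---|
| +2 | 75 | 50 | 25/75 = 33% |
| +1 | 50 | 37.5 | 12.5/50 = 25% |
| 0 | 37.5 | 25 | 12.5/37.5 = 33% |
| −1 | 25 | 12.5 | 12.5/25 = 50% |

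Because 5.1 bars re-escalation after a reduction, the difference can last for all remaining cycles.

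**The case against.** The best defense is that 5.1 is an overview and the subsections of 5.2 are the operative rules. The headings of 5.2.1 and 5.2.4 point that way, and 5.1 is phrased permissively: reductions are permitted, and patients are eligible to continue. On that reading 5.2.1 simply governs critical cytopenias. This is plausible, but the protocol does not say it, and 5.1 itself mentions cytopenias when it describes intolerance of the lowest dose. Nor does it settle 56 against 58 days, because 5.3 is a separate stopping rule. The 7-day allowance in section 5.6 concerns study visits and is not said to extend the 5.3 limit.

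It is also fair to say that an entry threshold and a retreatment threshold serve different purposes. A restart count below the entry count is not in itself a contradiction. The conflict arises only because 5.1 asks for return to baseline, and patient A depends on that patient's own pre-therapy count.

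A reader might infer more than the text supports:

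- **A four-way conflict among 5.1, 5.2.1, 5.2.4 and 5.3.** Sections 5.1 and 5.2.4 agree on return to baseline and a lower level. Section 5.3 sets only time limits. Sections 5.2.1 and 5.2.4 cover different toxicities, so their 56 and 58 days do not collide with each other.
- **That 5.1 would restart a patient with neutrophils of 600/mm³ at a lower level.** If baseline was 1000 or more, that patient does not meet the 5.1 condition and is not eligible to continue at any level.
- **That the primary analysis is affected.** Section 5.4 follows patients for relapse and death for three years from the first cycle, and section 3.5 does not list toxicity as an off-study reason. Although 5.2.1 and 5.2.4 speak of removal from the study, a different decision to stop treatment need not remove a patient from the relapse-free survival analysis. The futility rule (9.4) and the GVHD rule (9.5) use neither dose level nor hold length.

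**Conclusion.** The concern holds as two pairwise conflicts: 5.2.4 against 5.3 and 5.1 on the maximum hold, and 5.1 against 5.2.1 on recovery and restart level after critical cytopenia. The plan should be corrected, because following it as written can give different dosing or discontinuation decisions for the same patient.

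The hold conflict is narrow, affecting only events that resolve on day 57 or 58. The recovery conflict decides between continuing and not continuing. The restart conflict is one 5AC dose level, 25% to 50% of the dose, possibly for all remaining cycles.

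The recovery example assumes a pre-therapy neutrophil count at or above the entry minimum, and both cytopenia examples assume that 5.1 applies to critical cytopenias, which its wording allows and no text excludes. Frequency cannot be estimated: section 7.4 lists thrombocytopenia (66%) and neutropenia (32%) among 5AC reactions, but without grade, so these are not rates of critical cytopenia. The demonstrated effect is on consistency of dosing, treatment discontinuation and the toxicity summaries. None is shown on the relapse-free survival endpoint or the stopping rules.

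**What to change.** Reconcile the two pairs in one amendment.

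1. Reconcile 5.1 with 5.2.1. State which section governs critical cytopenias, with one recovery standard and one restart-level rule. If 5.1 is meant only as an overview, a sentence saying that the subsections of 5.2 take precedence would settle this pair.
2. Reconcile 5.2.4 with 5.1 and 5.3, so that one maximum hold applies throughout and agrees with the cycle-start window.

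The sponsor's clinicians choose the values; this review takes no view on which is right. If patients have already been treated, record for each toxicity hold which section was applied, so that dose levels and discontinuations can be reported consistently.

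The cost is a short protocol amendment. Sample size, endpoints and stopping boundaries do not change.

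### Section 5.2.1 joins the neutrophil and platelet recovery limits with 'or', so mixed recovery after a critical-cytopenia hold meets both restart rules, and a still-critical patient can meet the same-level rule

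*Combined protocol and SAP*

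**What the plan says.** Section 5.2.2 defines critical cytopenia as ANC below 100/mm³ or platelets below 10,000/mm³. Section 5.2.1 then holds both drugs and gives two restart rules:

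- ANC rises to 100–500, **or** platelets rise to 10,000–50,000: "the patient may resume the next cycle at the next lower dose level".
- ANC is above 500, **or** platelets are above 50,000: "the patient may resume the next cycle at the same dose level".

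If counts have not recovered adequately within 56 days of the first day of the latest cycle, the patient leaves the study and has a marrow examination.

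Section 5.1 carries a general rule. It covers "Patients who experience toxicity or dosing delays, but return to pre-therapy baseline" and says that those who do so "within 56 days of the first day of their most recent cycle, will be eligible to continue at the next lower Dose Level". It adds: "Patients requiring a dose reduction are not eligible for re-escalation". On escalation it says: "Patients who tolerate the combination with no SAEs during two consecutive cycles will be eligible for a dose escalation". The same section counts cytopenias among the reasons for not tolerating treatment (patients who cannot tolerate the lowest level "due to toxicities or cytopenias, will be removed from the study") and keeps patients at Level +2 "provided there are no toxicities requiring dosing delays or dose reduction". Section 7.2.1 refers physicians to 5.1 for escalation and de-escalation and does not mention 5.2.1.

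**The concern.** A dose rule applied after a marrow toxicity that the protocol itself calls critical should give one answer for each set of counts. With 'or' in both recovery sentences, a patient with one count in the middle band and the other above it fits both. Two investigators can each follow the text and give that patient different doses. A patient with one count still critical can also fit a restart sentence.

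These rules matter because marrow toxicity is controlled mainly through them. Section 7.2.1 names neutropenia as the reason why a higher 5AC schedule was poorly tolerated. The quantitative safety rule in section 9.5 is set for acute grade III/IV GVHD in the two transplant arms; otherwise there is only the general hold for unexpected serious toxicity in section 10.6. Section 9.4 accepts lenient futility rules partly because doses are adjusted for toxicity, and the toxicity profile is a secondary objective (section 1.2).

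A lesser question is how 5.1 and 5.2.1 fit together when counts return to baseline, and whether the hold cycle can count toward escalation.

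**Working it through.** The plan states no figure to reproduce. The check sets the rules against recovered counts and then sizes the dose difference from Table 2.

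**Step 1: the two sentences of 5.2.1 as written.** Lower-level sentence met if 100 ≤ ANC ≤ 500 or 10,000 ≤ platelets ≤ 50,000. Same-level sentence met if ANC > 500 or platelets > 50,000.

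| ANC (/mm³) | Platelets (/mm³) | Lower-level sentence | Same-level sentence |
|---|---|---|---|
| 300 | 30,000 | met | not met |
| 1,500 | 80,000 | not met | met |
| 1,500 | 30,000 | met | met |
| 300 | 80,000 | met | met |
| 600 | 5,000 (critical) | not met | met |
| 50 (critical) | 60,000 | not met | met |
| 300 | 5,000 (critical) | met | not met |

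Rows 3 and 4 are indeterminate. Rows 5 to 7 permit a restart with one count still critical under 5.2.2.

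**Step 2: does judging only the triggering lineage settle it?** The lower-level sentence speaks of a count that rises into the band, which points to the lineage that had been critical. If that reading is carried over to the same-level sentence, single-lineage holds are settled. Take a two-lineage hold, with ANC going from 50 to 1,500 and platelets from 5,000 to 30,000. Both lineages triggered and both rose; platelets meet the lower-level sentence and ANC meets the same-level sentence. If platelets stay at 5,000 while ANC reaches 600, ANC alone still meets the same-level sentence. Two-lineage holds remain unresolved.

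**Step 3: overlap with 5.1.** Section 3.1 requires ANC ≥ 1000 at entry. Taking baseline to mean entry counts, a critically neutropenic patient who is back at baseline has ANC > 500 and so meets the same-level sentence, while 5.1 names the next lower level and bars re-escalation. In the middle band (300/30,000, say) 5.2.1 also drops one level, so the two sections differ only after the better recovery.

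**Step 4: per-cycle dose, same level against next lower level (Table 2).** Level +2: 75/50 = 1.5. Level +1: 50/37.5 = 1.33. Level 0: 37.5/25 = 1.5. Level −1: 25/12.5 = 2.0.

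**Step 5: illustrative totals over 12 cycles of 5 days, with no later toxicity and no later escalation.**

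- Event in cycle 1 at Level 0. Same level: 5 × 12 × 37.5 = 2250 mg/m². Next lower: 5 × (37.5 + 11 × 25) = 1562.5 mg/m². Ratio 1.44.
- Event in cycle 6 at Level 0. 2250 against 5 × (6 × 37.5 + 6 × 25) = 1875 mg/m². Ratio 1.20.
- Event in cycle 5, the first at Level +2. Same level: 5 × (2 × 37.5 + 2 × 50 + 8 × 75) = 3875 mg/m². Next lower: 5 × (2 × 37.5 + 2 × 50 + 75 + 7 × 50) = 3000 mg/m². Ratio 1.29.

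**Step 6: escalation after a cycle-1 event with same-level restart, every optional escalation taken (upper bound).** Hold cycle counted: 5 × (2 × 37.5 + 2 × 50 + 8 × 75) = 3875 mg/m². Hold cycle not counted: 5 × (3 × 37.5 + 2 × 50 + 7 × 75) = 3687.5 mg/m². Ratio 0.952, about 5% less.

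**The case against.** **The sections do not contradict each other.** A reader might infer that 5.1 and 5.2.1 are in direct conflict, so that following one breaches the other. The text does not support that. Section 5.1 makes patients eligible for the lower level and 5.2.1 says that they may resume at the same level; these are two permissions. Section 5.2.1 is the specific hematologic rule with count limits, and reading 5.1 as mandatory would remove its same-level branch for patients back at baseline. The pointer in 7.2.1 calls 5.1 an outline and sets no precedence. This objection largely stands. What remains is that precedence is unstated and 5.1 itself mentions cytopenias.

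**The triggering lineage decides.** The 'rises to' wording supports this for the lower-level sentence. The same-level sentence lacks it, and two-lineage holds stay open (Step 2). Few clinicians would re-dose at platelets of 5,000, but a written safety rule should not permit it.

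**A critical-cytopenia cycle cannot count toward escalation.** A reader might infer that the plan lets such a patient escalate as if nothing had happened. The documents do not establish that. Escalation requires tolerance as well as no SAE, 5.1 links cytopenias to intolerance, and the SAE definition in section 10.5 includes important medical events, which could cover such counts. The objection mostly stands; the escalation sentence is merely not explicit.

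**The totals are hypothetical.** They are. Each assumes 12 completed cycles and a chosen event time, and every dose compared is an allowed Table 2 level.

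**Conclusion.** The 'or' in both recovery sentences of 5.2.1 is a real defect. It leaves the restart level open after mixed recovery, at least in two-lineage holds, and read literally it allows a same-level restart while one count is still critical. The unstated relation between 5.1 and 5.2.1 and the silence on hold cycles in the escalation test are secondary points of clarification.

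The size is a 1.33- to 2.0-fold difference in 5AC dose per cycle for an affected patient. The 1.44-fold cumulative figure illustrates an event in the first cycle and should not be read as an expected effect. The documents give no rate of critical cytopenia, so the number of patients affected is unknown. A reader might also infer harm to the trial's power or stopping rules, but no stated sample size or operating characteristic depends on this point.

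The conclusion rests on a literal reading of 'or'. Step 3 also takes baseline to mean the counts at entry.

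**What to change.** 1. In 5.2.1, replace the two recovery sentences with three rules. Same level only if ANC > 500/mm³ **and** platelets ≥ 50,000/mm³. Next lower level if ANC ≥ 100 and platelets ≥ 10,000 but either count falls short of the same-level limits. Otherwise the hold continues, up to the existing 56-day limit. Using ≥ 50,000 rather than > 50,000 avoids failing a patient who is back at the entry platelet minimum, on the assumption that the printed 50 in section 3.1 means 50,000/mm³.
2. In 5.1, state that 5.2.1 sets the restart level after any hold or delay for cytopenia, critical or not, and that the next-lower-level rule in 5.1 applies to non-hematologic toxicity. Limiting the reference to critical cytopenia would be worse: a milder cytopenia delay would then force a reduction while a critical one kept its dose.
3. In 5.1, state that a cycle with a critical cytopenia or a toxicity-related hold does not count toward the two cycles needed for escalation.

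Under rule 1, 1,500/30,000 and 300/80,000 go to the lower level, 1,500/80,000 restarts at the same level, and 600/5,000, 50/60,000 and 300/5,000 stay on hold.

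The cost is a short rewrite of 5.2.1 and two sentences in 5.1. No new data are needed, since Table 4 already schedules a blood count on day 1 of each cycle. Some patients with mixed recovery go to the lower level without re-escalation. They include some whose low lineage did not trigger the hold, such as a neutropenia-only hold with platelets at 45,000. Some escalations come about one cycle later (3687.5 against 3875 mg/m² in the upper-bound case).

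### Section 5.1 gives children a flat 125 micrograms/day of GM-CSF; below 1.0 m² of body surface area this exceeds both Table 3 and the 125 micrograms/m² maximum in Section 2.1

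*Combined protocol and SAP*

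**What the plan says.** The visible text bears on the pediatric GM-CSF dose in four places.

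- **Section 5.1, text.** After the 70 kg weight bands (125 or 250 micrograms/day), the plan adds: "Pediatric subjects will receive 125 micrograms/day regardless of weight".
- **Section 5.1, Table 3.** The column for patients aged 18 or under reads "125micrograms/ m² x10D" at Level 0, "62.5micrograms/ m ² x10D" at Level -1 and "50micrograms/ m ² x 10D" at Level -2. Level -3 is 50 micrograms/m² for 7 days. The Level 0 cell carries a footnote mark whose text is not visible. No pediatric entry is visible at Level +1; the over-18 entry there is "250 micrograms (starting dose weight >70 kg) x 10D".
- **Section 2.1.** The pediatric paragraph names 125 micrograms/m² as the proposed maximum allowable dose and says that higher doses were tolerated with limited toxicity in earlier pediatric studies.
- **Section 7.2.2.** The dosing rationale repeats the 70 kg bands and gives no pediatric rule.

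Section 3.1 admits patients from 0.5 years of age. On dispensing, Section 5.1 says: "Subjects will be given prescriptions for pre-dosed syringes of GM-CSF".

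**The concern.** The text and the table in one section give a child two different starting doses, in different units. Nothing visible says which governs. A flat dose that ignores body size gives the most drug per square metre to the smallest patients, and eligibility extends to infants. In those patients the Section 5.1 sentence exceeds a limit that the protocol sets for itself.

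The practical risk is in dispensing. Two competent pharmacists could fill the same order differently, by a factor of two or three in the smallest eligible children. Because the syringes are pre-dosed, the choice carries through a 10-day course. The safeguards (holding the drug for side effects or a white count above 25,000, and weekly blood counts in the first cycle) act only after dosing has begun.

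**Working it through.** **Inputs from the protocol.** Flat pediatric dose 125 micrograms/day (Section 5.1 text). Pediatric Level 0 dose 125 micrograms/m²/day and Level -1 dose 62.5 micrograms/m²/day, each for 10 days (Table 3). Proposed maximum 125 micrograms/m² (Section 2.1). Youngest eligible age 0.5 years (Section 3.1).

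**Assumption.** The protocol gives no BSA values, so a range from 0.33 to 2.0 m² is shown.

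**Formulas.**

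- Flat dose per m² = 125 / BSA
- Table 3 Level 0 daily dose = 125 × BSA
- Ratio of flat dose to Table 3 Level 0 = 125 / (125 × BSA) = 1/BSA. The Section 2.1 maximum has the same per-m² value, so the ratio to that maximum is also 1/BSA.
- Table 3 Level -1 daily dose = 62.5 × BSA

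| BSA (m²) | Flat 125 expressed per m² | Table 3 Level 0 (micrograms/day) | Flat ÷ Level 0 | Table 3 Level -1 (micrograms/day) |
|---|---|---|---|---|
| 0.33 | 379 | 41.2 | 3.0 | 20.6 |
| 0.50 | 250 | 62.5 | 2.0 | 31.2 |
| 0.75 | 167 | 93.8 | 1.3 | 46.9 |
| 1.0 | 125 | 125 | 1.0 | 62.5 |
| 1.5 | 83 | 187.5 | 0.67 | 93.8 |
| 1.7 | 73.5 | 212.5 | 0.59 | 106 |
| 2.0 | 62.5 | 250 | 0.50 | 125 |

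Over one 10-day course, the flat rule gives 10 × 125 = 1250 micrograms at every size. Table 3 Level 0 gives 10 × 62.5 = 625 micrograms at 0.50 m² and about 412 micrograms at 0.33 m².

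**Could the unseen footnote remove the conflict below 1.0 m²?** There are two plausible readings.

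1. It caps the dose at 125 micrograms/day. Level 0 is then the lesser of 125 × BSA and 125. Below 1.0 m² the lesser value is 125 × BSA, so the cap never applies and the conflict stands. At 1.0 m² or more the capped dose is 125, which matches Section 5.1.
2. It says that children start on a flat 125. Section 5.1 and Table 3 then agree, but below 1.0 m² Level 0 is still 1/BSA times the Section 2.1 maximum.

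**Reduction from a 125 microgram start above 1.0 m².** The cut on moving to Level -1 is 1 - (62.5 × BSA)/125 = 1 - BSA/2. That is 25% at 1.5 m², 15% at 1.7 m² and 0% at 2.0 m². This matters only if such a child starts at 125 micrograms, by the Section 5.1 rule or by a cap, and is then reduced by Table 3.

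**The case against.** The best defence is that the intended unit is fairly clear. Section 2.1 and all four pediatric rows of Table 3 are per m². The Section 5.1 sentence directly follows the adult weight bands, so it can be read as saying only that children never move up to the 250 microgram dose above 70 kg. The absence of a visible pediatric Level +1 entry fits that reading. It is plausible, and with the footnote it could reconcile the starting doses above 1.0 m². It does not help below 1.0 m², because the sentence as written sets a dose and not a ceiling.

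Other points on this side also have force. Section 2.1 reports that children tolerated higher doses, which limits the likely harm but does not resolve the contradiction. Section 9 describes the study as one in adults and projects no pediatric accrual, so few children may be affected. Below 1.0 m², a first reduction from flat 125 is steep (75% at 0.50 m²), but it lands on the intended Table 3 Level -1 and so corrects the dose. Section 5.2.1 says that "the patient may resume the next cycle at the next lower dose level" without naming which drug's level is meant, so it is weak evidence of a GM-CSF reduction.

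Three stronger readings are tempting, and the documents do not support them.

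- **That the rules can agree only at exactly 1.0 m².** This is true of the printed figures, but the unseen footnote may be a cap that makes them agree at every size from 1.0 m² upward.
- **That the flat dose exceeds published pediatric experience.** Section 2.1 gives no upper figure for that experience, so only the breach of the protocol's own maximum can be shown.
- **That Levels -1 to -3 should be rewritten as fractions of a capped start.** Those entries are clear per-m² doses with no visible footnote, and nothing in the protocol supports replacing them.

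**Conclusion.** The point holds for children below 1.0 m². There, the Section 5.1 sentence contradicts Table 3 and breaches the Section 2.1 maximum by a factor of 1/BSA. Neither plausible reading of the unseen footnote brings the Section 5.1 dose within that maximum. The factors of 1.3, 2.0 and 3.0 rest on assumed BSA values; the direction and the 1/BSA relation do not.

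Above 1.0 m² the finding is weaker: the printed starting doses differ, but they may be reconciled by text that is not visible.

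This is an internal inconsistency in a dosing instruction, and it should be corrected before a child is dosed under it. The number of children exposed is unknown.

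**What to change.** Replace the pediatric sentence in Section 5.1 with wording such as: *Patients aged 18 years or under will start at 125 micrograms/m²/day (Table 3) on days 1-10; the 70 kg weight bands apply only to patients over 18 years.* Repeat the rule in Section 7.2.2.

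If the existing sentence was meant as a ceiling, add *to a maximum of 125 micrograms/day*, with the sponsor confirming the figure against the Table 3 footnote.

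Keep Levels -1 to -3 per m². If a 125 microgram cap is adopted, the sponsor should check that each level is still a real reduction for large adolescents, because Level -1 is 62.5 × 1.7 = 106 micrograms at 1.7 m² and 62.5 × 2.0 = 125 micrograms at 2.0 m².

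The cost is a short amendment, one sponsor decision on the cap and an updated pharmacy order. Design, sample size and analysis do not change.
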